3. Cirrhosis and ascites.
4. No sustained improvement in renal function (less than 20% decrease in SCr) at least 48 hours after diuretic withdrawal and after plasma volume expansion with albumin (given daily for two days - 48 hours minimum from 1st dose). If SCr improves by \geq 20 % but plateaus (\leq 10 % fluctuation in sCr) and remains above 1.5 mg/dl for \geq another 48 hrs and there are no features of acute tubular necrosis.
5. Increase in SCr by at least \geq 0.3 mg/dl OR 1.5-2 fold above baseline (AKI stage 1 and above), to a SCr of \geq 1.5 mg/dl at the time of initiating treatment. Baseline SCr is defined as the most recent, lowest SCr within last 6 months before date of current admission.
6. A.) On liver transplant wait list or liver transplant eligible with anticipation of being placed on the liver transplant wait list. B.) Patients not on the transplant waitlist or transplant eligible are also eligible for the trial (maximum 25 subjects)

Exclusion Criteria:

1. Serum creatinine level greater than 5.0 mg/dL. Subjects with value greater than 5.0 mg/dL may be enrolled with Sponsor prior approval.
2. MELD score of \geq 35
3. Acute on Chronic Liver Failure (ACLF) grade 3 (according to the CLIF Consortium grading system)
4. Uncontrolled sepsis and/or uncontrolled bacterial infection (e.g., persisting bacteremia, persisting ascitic fluid leukocytosis, fever, increasing leukocytosis with vasomotor instability).
5. Shock.
6. Current or recent (within 4 weeks) treatment with or exposure to nephrotoxic agents: e.g., aminoglycosides, amphotericin, cyclosporine A, cisplatin, nonsteroidal anti-inflammatory drugs (NSAIDs: e.g., ibuprofen, naproxen, diclofenac), significant exposure to radiographic contrast agents (large doses or multiple injections of iodinated contrast media; e.g., during coronary or abdominal angiogram).

Collaborative Research Study, Version 4: 06/29/21
To Treat HRS-AKI Patients with Continuous Terlipressin Infusion

7. Estimated life expectancy of less than 7 days.
8. Advanced hepatocellular Carcinoma with expected life expectancy of < 6 months
9. Superimposed acute liver injury due to drugs (e.g., acetaminophen), dietary supplements, herbal preparations, viral hepatitis, or toxins (e.g., Amanita toxin with mushroom poisoning carbon tetrachloride), with the exception of acute alcoholic hepatitis.

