Dosing for M&O, albumin, or other vasopressor will be reported as it was recorded on the subject's chart.

For Prospective Terlipressin Group:

Terlipressin will be supplied in single-use, sterile 6-mL vials containing 1 mg of lyophilized Terlipressin acetate (equivalent to 0.85 mg Terlipressin free base) with 10 mg mannitol as a bulking agent/stabilizer.

Initial Dosing:

Terlipressin will be administered intravenously as a bolus injection (the vial will be reconstituted with 5 mL of sterile 0.9% sodium chloride solution and given over 1 minute at a dose of 0.5 mg).

- Continued dosing will be by 2 mg infusion per day. For continuous infusion, the dose of terlipressin is to be dissolved in 0.9% sodium chloride solution and infused with a pump.

Dose Modifications:

- If on Day 3 the SCr is not 30% lower from the baseline value, increase infusion dose to 4 mg per day.
- If on Day 5 the SCr is not 50% lower from the baseline value, increase infusion dose to 6-8 mg per day, per PI discretion. Dosing can be increased by more than 1 mg increment at Day 5 or beyond, up to a maximum of 8 mg/day.
- If the subject has infusion stopped for \geq 4 hours, a 0.5 mg bolus should be given prior to restarting infusion.
- The drug should not be used in subjects with severe coronary artery disease or in the setting of circulatory overload, pulmonary edema, or bronchospasm as determined by the Investigator. If drug therapy has been initiated, Investigator can also decide not to increase the dose, based on the patient's status with regard to the above, based on individual subject condition.

Collaborative Research Study, Version 4: 06/29/21
To Treat HRS-AKI Patients with Continuous Terlipressin Infusion

- If dosing is interrupted due to an adverse event, terlipressin may be re-started, at the discretion of the investigator, at the same or lower dose as per protocol. Terlipressin will not be restarted if dosing was interrupted due to cardiac ischemia or mesenteric ischemia.

Treatment Discontinuation:

- Terlipressin may be continued until 24 hours after serum creatinine has reached the lowest value possible as determined by Principal Investigator, up to a maximum of 14 days.
- After a minimum of 72 hours post final dose escalation and tolerability, if the SCr is at or above enrollment value, terlipressin should be discontinued.

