8.4 Administration

Subjects in the Prospective Terlipressin Group:

Single-use, sterile 6-mL vials containing 1 mg of lyophilized terlipressin acetate (equivalent to 0.85 mg terlipressin free base) with 10 mg mannitol as a bulking agent/stabilizer.

- For initial bolus dose of 0.5mg, the vial will be reconstituted with 5 mL of sterile 0.9% sodium chloride solution and given over 1-minute push.
- Continued dosing will be by 2mg infusion per day for Days 1, and 2. For continuous infusion, the dose of terlipressin is to be dissolved in 0.9% sodium chloride solution and infused with a pump.
- If on Day 3 the SCr is not 30% lower from the baseline value, increase infusion dose to 4 mg per day.
- If on Day 5 the SCr is not 50% lower from the baseline value, increase infusion dose to 6-8 mg per day, per PI discretion. Dosing can be increased by more than 1 mg increment at Day 5 or beyond, up to a maximum of 8 mg/day.
- If the subject has infusion stopped for \geq 4 hours, a 0.5 mg bolus should be given prior to restarting infusion.
- The drug should not be used in subjects with severe coronary artery disease or in the setting of circulatory overload, pulmonary edema, or bronchospasm as determined by the Investigator. If drug therapy has been initiated, Investigator can also decide not to increase the dose, based on the patient's status with regard to the above, based on individual subject condition.

- If dosing is interrupted due to an adverse event, terlipressin may be re-started, at the discretion of the investigator, at the same or lower dose as per protocol. Terlipressin will not be restarted if dosing was interrupted due to cardiac ischemia or mesenteric ischemia.

Subjects in the Retrospective Control Group:

The dose and method of administration for Midodrine/Octreotide (M&O), albumin, or other vasopressor will be recorded as noted in the patient's medical record. To be included as a completed subject in this study, patients must have been treated for at least 48 hours with albumin infusions beyond volume resuscitation and diuretic withdrawal. Vasopressors also need to be used for a minimum of 48 hours.

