Record RRT, TIPS, transplant, and mortality ^j			Monitor and record throughout active study period and follow-up.																		
Record all paracentesis events			Record all paracentesis performed until drug treatment discontinued																		

Collaborative Research Study, Version 4: 06/29/21
To Treat HRS-AKI Patients with Continuous Terlipressin Infusion

All assessments are completed per Standard of Care.

^aMaximum treatment of 14 Days.

^bFemale subjects of child-bearing potential must have a negative urine or serum pregnancy test within 14 days prior to the first dose of study treatment.

^cThe qualifying SCr value (SCr value at least 48 hours after both diuretic withdrawal and the beginning of albumin fluid challenge) is considered the Enrollment SCr and must be drawn prior to start of study drug. The qualifying SCr value must be ≥ 1.5 mg/dL AND Baseline SCr is defined as the most recent, lowest SCr within last 6 months before date of current admission.

^dA general standard of care physical assessment of the major body systems evaluating any new clinically significant abnormalities within the following: general appearance, skin, head/eyes/ears/nose/throat, neck, heart, lungs, abdomen, extremities, and neurological systems. The investigator may perform additional unscheduled examinations to manage or evaluate a suspected AE as clinically necessary. The physical examination will also include weight and height.

^eCollection of the data from the last electrocardiogram done prior to admission and the electrocardiogram performed during admission, if performed as per standard of care

^fMust be performed at least once daily during active treatment AND until Day 14 (regardless of treatment status) or discharge, whichever occurs first. BUN & eGFR are recorded if taken per site standard of care. If assessments are performed more than once daily as part of the subject's medical care, all values are to be recorded on the CRF. If subject has SCr, BUN and/or eGFR, including Vital signs taken at any of the Follow-up Periods, they are to be recorded on the CRF.

^gSerious Adverse Events will be required to be collected only for the Prospective Terlipressin Group.

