10.3 Active Study Period (14 Days)

Dosing (Up to 14 Days)

The active study period extends from the initiation of study treatment through Day 14 or discharge from the hospital for any reason, whichever occurs first. Study drug will be administered as described in Section 7.3.2. Concomitant medications will be collected during this active study period. See Table 8.1 for the schedule of assessments during the active study period.

End of Treatment, Discharge or Day 14

Terlipressin may be continued until 24 hours after serum creatinine has reached the lowest value possible as determined by Principal Investigator, up to a maximum of 14 days.

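### The Day 3 and Day 5 dose-escalation tests refer to a baseline creatinine that, as defined, is the pre-admission value and not the value at the start of treatment

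*Combined protocol and SAP*

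**What the plan says.** The escalation tests appear in the synopsis under Dose Modifications and again in section 8.4.

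- **Day 3** (synopsis): "If on Day 3 the SCr is not 30% lower from the baseline value, increase infusion dose to 4 mg per day". Section 8.4 uses the same condition: "If on Day 3 the SCr is not 30% lower from the baseline value".
- **Day 5** (synopsis): "If on Day 5 the SCr is not 50% lower from the baseline value", the infusion goes to 6-8 mg per day at the investigator's discretion.

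Neither place says which creatinine value is meant. The term is defined in inclusion criterion 5 (synopsis and section 7.3) and in Table 1 footnote c: "Baseline SCr is defined as the most recent, lowest SCr within last 6 months before date of current admission".

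Footnote c gives the pre-dose value a different name. The qualifying value, taken no earlier than 48 hours after diuretics are stopped and albumin is begun, "is considered the Enrollment SCr and must be drawn prior to start of study drug". The synopsis stopping rule uses that second term: it compares SCr with the enrollment value.

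Other sections use 'baseline' for the pre-treatment assessment: the Table 1 Baseline Assessment column, section 10.2, section 11.3 (MELD), section 12.2 (which glosses it as pretreatment for the optional samples) and section 13.1.

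**The concern.** One word has two meanings, and the dosing rule does not say which applies. A reader who follows the written definition has some textual support, because the same synopsis dosing text uses the enrollment value for stopping and the baseline value for escalating. That contrast could be taken as deliberate.

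What is at stake is the dose of a vasoconstrictor. Inclusion criterion 5 requires SCr to have risen above the defined baseline, so the defined reading is always the stricter one. A subject who responds well from the start of treatment can pass both tests on one reading and fail both on the other. Two sites could then dose the same creatinine course differently, each with a defensible reading of the protocol.

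**Working it through.** The plan gives no figure of its own to reproduce here. The check is to compute the escalation cut-offs under each reading.

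**Inputs.** The 30% and 50% tests and the 2, 4 and 6-8 mg/day steps come from the synopsis and section 8.4. B is the pre-admission value and E is the Enrollment SCr. The documents give no typical values of either, so all values below are assumed for illustration.

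**Step 1: cut-offs to avoid escalation.** On the pre-dose reading they are 0.7E (Day 3) and 0.5E (Day 5). On the defined reading they are 0.7B and 0.5B. The readings disagree on Day 3 when SCr lies above 0.7B but at or below 0.7E, and on Day 5 when it lies above 0.5B but at or below 0.5E.

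**Step 2: fall from E needed on the defined reading.** This is 1 - 0.7B/E on Day 3 and 1 - 0.5B/E on Day 5. On the pre-dose reading it is always 30% and 50%.

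| B, E (mg/dL) | Rise | Day 3 | Day 5 |
|---|---|---|---|
| 1.2, 1.5 | 1.25-fold | 1 - 0.84/1.5 = 44% | 1 - 0.60/1.5 = 60% |
| 1.0, 1.5 | 1.5-fold | 1 - 0.70/1.5 = 53% | 1 - 0.50/1.5 = 67% |
| 1.0, 2.0 | 2-fold | 1 - 0.70/2.0 = 65% | 1 - 0.50/2.0 = 75% |

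**Step 3: a subject fully back at B.** On the defined reading the fall below baseline is 0%, so both tests are failed whatever the rise. On the pre-dose reading the fall is 1 - B/E. It reaches 30% only if E/B is at least 1/0.7 = 1.43, and 50% only if E/B is at least 1/0.5 = 2. Below those ratios both readings escalate. For example, a return from 1.5 to 1.2 is a fall of 1 - 1.2/1.5 = 20%, which fails both tests on either reading.

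**Step 4: one illustrative subject.** Take B = 1.0, E = 2.2, Day 3 SCr 1.4 and Day 5 SCr 1.0 mg/dL, with the same creatinine course under either dose.

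- Pre-dose reading: cut-offs are 0.7 × 2.2 = 1.54 and 0.5 × 2.2 = 1.10. The falls are 1 - 1.4/2.2 = 36% and 1 - 1.0/2.2 = 55%. Both tests are passed and the dose stays at 2 mg/day.
- Defined reading: cut-offs are 0.70 and 0.50. SCr is 40% above baseline on Day 3 and equal to it on Day 5. Both tests are failed.

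Suppose Day 5 is the lowest value and the infusion stops 24 hours later, at about Day 6, with no investigator hold and the bolus excluded. The infusion total is 6 × 2 = 12 mg on the pre-dose reading. On the defined reading it is 2 × 2 + 2 × 4 + 2 × (6 to 8) = 24 to 28 mg, or 2 × 2 + 4 × 4 = 20 mg if only the Day 3 step is taken.

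**The case against.** The strongest reply is that nobody would apply the literal definition. It asks for creatinine 30% below the lowest pre-admission value by Day 3 and half of it by Day 5, which makes little clinical sense. The 6-month definition sits with the AKI entry test, and the on-study sections use 'baseline' for the pre-treatment draw. This stands as an account of intent. It does not change the fact that the term is formally defined the other way wherever it is defined.

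A second reply is that clinical judgement protects the subject. The Day 5 step is at the investigator's discretion, the "Investigator can also decide not to increase the dose", and "Terlipressin may be continued until 24 hours after serum creatinine has reached the lowest value possible as determined by Principal Investigator". These limit the consequence. However, the permission to hold refers back to coronary disease, circulatory overload, pulmonary edema or bronchospasm, allowing for the individual subject's condition. The Day 3 step has no discretion wording of its own. None of these provisions names the comparison value.

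A third reply is that the illustrative subject is favourable to the point: the assumed rise is 2.2-fold, and on Day 3 the subject is still 40% above the pre-admission value. That is fair. The Day 3 step in this example escalates a responder, already below the 1.5 mg/dL that section 3.3 uses for HRS reversal, but not someone fully recovered.

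A reader might infer that the pre-dose reading spares every recovered subject from escalation. Step 3 shows that it does not when the rise was below 1.43-fold (Day 3) or 2-fold (Day 5), and entry permits such rises.

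**Conclusion.** The inconsistency is real and lies in a dosing rule, so it should be corrected. The pre-dose reading is almost certainly what was meant. Applied as defined, the tests raise the required fall from Enrollment SCr from 30%/50% to 44%/60% after a rise from 1.2 to 1.5 mg/dL, and to 65%/75% after a 2-fold rise. Responders who fall short of those figures would be escalated unless the investigator holds the dose.

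The formulas follow from the protocol text. The creatinine values and dose totals are illustrative. The documents give no distribution of response, so the share of subjects affected cannot be stated.

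Two stronger conclusions are tempting but unsupported. One is that sites will dose, or have dosed, differently: the documents contain no evidence either way. The other is that the primary analysis is compromised because section 15.1 adjusts for a baseline SCr that it does not specify. That section also enters all potential confounders before removing any, so starting creatinine would be kept if it is a candidate and matters. Naming the covariate there is only a clarification. The same holds for the 50% reduction in Retreatment, which most naturally means a fall from the start of treatment.

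**What to change.** In the synopsis Dose Modifications and in section 8.4, replace the reference to the baseline value in both tests with: the Enrollment SCr (qualifying value before study drug, Table 1 footnote c). This matches the stopping rule. One value should be named, because Table 1 schedules SCr at both Screening and the Baseline Assessment and the two results can differ.

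Rename the 6-month value *pre-admission SCr* in inclusion criterion 5 (synopsis and section 7.3) and in footnote c.

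Optionally, use the same named value for the 50% test in Retreatment and for the covariate in section 15.1.

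The cost is a wording amendment and a notice to sites. Prospective subjects already need both values for eligibility, so no new measurement is required. The change removes the ambiguity only. If the sponsor also wants to avoid escalating recovered subjects whose initial rise was small, that needs a separate rule.

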18.2 PROTOCOL AMENDMENTS	56
18.3 INFORMED CONSENT.....	56
18.4 CONFIDENTIALITY	56
18.5 SUBJECT INJURY	57
SUBJECT INJURY PROVISIONS WILL BE SPECIFIED IN THE SITE'S CLINICAL TRIAL AGREEMENT.....	57
18.6 STUDY SUSPENSION, TERMINATION, AND COMPLETION.....	57
18.7 STUDY AND STUDY SITE DISCONTINUATION CRITERIA.....	57
19 REGISTRATION OF STUDY AND PUBLICATION OF DATA	58
19.1 INVESTIGATOR'S ABILITY TO PUBLISH	58
20 REFERENCES	59
21 APPENDIX A: TERLIPRESSIN STABILITY DATA:	63
22 APPENDIX B: SODIUM CHLORIDE SOLUTION:	67
23 APPENDIX C: TERLIPRESSIN MICROBIOLOGY	68

2 List of Abbreviations

Abbreviation	Definition
AASLD	American Association for the Study of Liver Diseases
ACLF	acute on chronic liver failure
AE	adverse event
AKI	acute kidney injury
ALP	alkaline phosphatase
ALT	alanine amino transferase, also known as SGPT
ANCOVA	analysis of covariance
AR	adverse reaction
AST	aspartate amino transferase, also known as SGOT
BUN	blood urea nitrogen
CBC	complete blood count
CFR	Code of Federal Regulations
CMH	Cochran-Mantel-Haenszel
CrCl	creatinine clearance
CRF	Case report form
EASL	European Association for the Study of the Liver
ECG	Electrocardiogram
eGFR	estimated glomerular filtration rate
EVH	esophageal variceal hemorrhage
FDA	Food and Drug Administration
GCP	Good Clinical Practice
HRS	hepatorenal syndrome
IAC	International Ascites Club
IAC-AKI	IAC-acute kidney injury
IB	Investigator's Brochure
ICF	informed consent form
ICH	International Conference on Harmonization
IME	important medical events
IND	Investigational New Drug
INR	international normalized ratio
IRB	Institutional Review Board
ITT	intent to treat
IV	Intravenous
LAR	Legally Authorized Representative
LVP	large volume paracentesis
MAP	mean arterial pressure

**Collaborative Research Study, Version 4: 06/29/21
To Treat HRS-AKI Patients with Continuous Terlipressin Infusion**

Abbreviation	Definition
MedDRA	Medical Dictionary for Regulatory Activities
MELD	model for end-stage liver disease
M&O	Midodrine/Octreotide
NDA	New Drug Application
NSAID	nonsteroidal anti-inflammatory drug
RBC	red blood cell
RRT	renal replacement therapy
SAE	serious adverse event
SUSAR	suspected unexpected adverse reaction
SCr	serum creatinine
SIRS	systemic inflammatory response syndrome
SOC	standard of care
SpO ₂	pulse oximetric saturation
SRO	Safety Review Officer
TIPS	transjugular intrahepatic portosystemic shunt
US	United States
WBC	white blood cell
WHO	World Health Organization

3 Introduction

3.1 Hepatorenal Syndrome

Hepatorenal syndrome (HRS) Type 1, a potentially reversible renal failure, is a serious, rapidly progressing, fatal orphan disease complicating decompensated chronic liver disease associated with cirrhosis (Arroyo, 1996; Salerno, 2007; Angeli, 2015). The estimated United States (US) annual incidence for HRS Type 1 ranges between 9,000 and 20,000 patients (Marrero, 2003; Muir, 2002; Murkerjee, 2002; National Hospital Discharge Survey 2005), establishing it as an orphan disease. The death rate from chronic liver disease and cirrhosis has been rising, while the death rates for other major diseases such as stroke, cancer, heart disease, and diabetes have gone down in the past 15 years (Centers for Disease Control and Prevention 2013; Ma, 2015).

As indicated in the American Association for the Study of Liver Diseases (AASLD) Guidelines, at present, there is no available pharmacological therapy (i.e., approved or proven) in the US or Canada for HRS Type 1 (Runyon, 2013) and there remains a significant unmet need.

An increasing body of knowledge of the pathophysiology of HRS Type 1 has demonstrated that vasoconstrictive drug therapy may improve renal function in HRS Type 1 (Salerno, 2007; European Association for the Study of the Liver 2010). Terlipressin has been extensively studied as a splanchnic vasoconstrictor for the treatment of HRS Type 1 and is the standard of care for this condition wherever the drug is available (European Association for the Study of the Liver 2010). Although there has been some off-label use of other vasoconstrictors, a recent study has shown that the most commonly used agents (i.e., combination of midodrine and octreotide) are not effective (Cavallin, 2015).

There is a shift in HRS terminology to move away from HRS Type 1 and HRS Type 2 to the new designations of HRS-Acute Kidney Injury (HRS-AKI) and HRS-Chronic Kidney Disease (HRS-CKD), respectively, in order to better harmonize with the existing nomenclature in nephrology, the clinical consequences of kidney injury, and initiation of treatment at earlier time points when it is more effective (Angeli, 2015). HRS-AKI removes the condition of creatinine doubling over two weeks, as often patients with ascites, a precipitating event, and HRS physiology may not have had a creatinine checked in the preceding two weeks but would still benefit from HRS treatment. Additionally, HRS-AKI divides the kidney injury into stages (1-3) to mirror the AKI criteria set forth by the Acute Kidney Injury Network (AKIN) (Angeli, 2015).

3.2 Terlipressin

Terlipressin is a synthetic vasopressin analogue that acts as a systemic vasoconstrictor via the vascular vasopressin V₁ receptors. In HRS patients the strong V₁ receptor-mediated vasoconstrictor activity of terlipressin, particularly in the splanchnic area, increases effective intravascular volume and mean arterial pressure (MAP), ameliorates renin-angiotensin-aldosterone system and sympathetic nervous system hyperactivity, and improves renal blood flow. These corrective hemodynamic effects culminate in improved renal function, thereby providing the pharmacologic rationale for treatment of HRS with terlipressin (Arroyo, 2000; Ginès, 2003; Kiszka-Kanowitz, 2004).

After intravenous (IV) administration of terlipressin, the glycyl residues of terlipressin are cleaved by endogenous tissue proteases. Thus, terlipressin levels in the blood decrease rather rapidly and the pharmacologically active metabolite lysine-vasopressin is released gradually from tissues into the circulation. Intravenous terlipressin can be delivered quickly via bolus injection or slowly through continuous infusion. There is evidence that continuous infusion leads to fewer adverse events and lower total terlipressin doses to achieve HRS reversal (Cavallin, 2016). A bolus injection prior to continuous infusion will achieve therapeutic levels earlier than continuous infusion alone.

Terlipressin is approved in many countries and regions outside the US where it has been a standard of care for decades in the treatment of subjects with liver cirrhosis and esophageal variceal hemorrhage (EVH) (de Franchis, 2005; Ioannou, 2003), and has more recently become a standard of care for the treatment of subjects with HRS Type 1 where it is available (EASL, 2010). Terlipressin has been approved for the treatment of HRS Type 1 in Australia, France, Ireland, South Korea, Mexico, Taiwan, Spain, India, Brazil, Turkey, and Portugal.

